# 3.3.2 Handling of Participant Withdrawals and Participant Discontinuation of Study Intervention

Replacement of participants who withdraw or discontinue early in the study will be allowed.

#### 3.4 Premature Termination or Suspension of Study

This study may be suspended or prematurely terminated if there is sufficient reasonable cause. Written notification documenting the reason for study suspension or termination will be provided by the suspending or terminating party to the funding sponsor. If the study is prematurely terminated or suspended, the principal investigator will promptly inform the IRB and will provide the reason(s) for the termination or suspension.

Circumstances that may warrant termination include, but are not limited to:

- Determination of unexpected, significant, or unacceptable risk to participants.
- Insufficient adherence to protocol requirements.
- Data that is not sufficiently complete and/or evaluable.

# 4 Study Intervention

# 4.1 Study Product

Fitbit Inspire HR

# 4.2 Study Product Description

The Fitbit Inspire HR is a band based fitness tracker with a 0.8 inch monochrome, OLED, touchscreen display. The battery life is approximately 5 days. It has the following sensors: 3-axis accelerometer, optical heart rate monitor, vibration monitor. It includes inactivity alerts. Its dimensions are 1.5 inches x 0.6 inches. The Fitbit is not intended to be used as a medical device.

The Fitbit Inspire HR syncs automatically an wirelessly to 200+ leading iOS, Android, and Windows 10 devices using Bluetooth LE wireless technology. It syncs with iPhone 4S and later, iPad 3 generation and later, Android 5.0 and later, and Windows 10 devices. Syncing requires Bluetooth LE and internet connection.

#### 4.2.1 Acquisition

The study product will be acquired directly from the manufacturer.

# 4.3 Study Product Accountability

The study product will be distributed to patients who meet the inclusion/exclusion criteria after enrollment. Each participant will receive one wearable device that will be paired with a centralized data aggregation platform to automatically collect and store data. After completion of the study, participants will be able to keep the wearable device they used in the study.

### 4.4 Assessing Participant Compliance with Study Product Administration

Compliance with the wearable device will be assessed at each outpatient visit and using the centralized data aggregation platform.

#### 4.5 Concomitant Medications/Treatments

There are no restrictions on concomitant medications/treatments.

#### 4.6 **Dietary Restrictions**

There are no dietary restrictions for participants during the trial.

# 5 Study Schedule

# 5.1 Screening

# Screening Visit (can occur up to 28 days prior to enrollment or on the same day as enrollment)

The scope of the study will be explained to the patient prior to any screening during the informed consent. Patients should be asked to sign and date a Notice of Privacy Practice research authorization/HIPAA form and an IRB-approved statement of informed consent that meets the requirements of the Code of Federal Regulations (Federal Register Vol. 46, No. 17, January 27, 1981, part 50). During the screening period, subject eligibility will be determined according to the inclusion and exclusion criteria. The following assessments will be performed during this time:

- Review medical history to determine eligibility based on exclusion/inclusion criteria.
- Obtain informed consent from the potential participant.
- Perform medical examination needed to determine eligibility
- Record any current medications
- Assess ECOG performance status

#### 5.2 Enrollment/Baseline

#### **Enrollment/Baseline Visit**

- Obtain/verify consent from participant on study consent form
- Verify inclusion/exclusion criteria
- Obtain demographic information, medical history, medication history, and social history
- Perform and record physical examination
- Assess ECOG Performance Status
- Provide patient with Fitbit Inspire HR wearable activity monitoring device with instruction on proper usage/operation.
- Ensure proper pairing and functionality with centralized data aggregation platform
- Assess baseline anemia-related symptoms using FACT-An questionnaire.
- Check baseline CBC

#### 5.3 Treatment Period

### Two times per week

- Check CBC
- Administer Fact-An

#### Office visits per standard of care (to be determined by the patient's physician)

- Record results of physical examination, vital signs
- Assess any new medications
- Assess ECOG performance status
- Record participant's compliance with wearing Fitbit Inspire HR device

# 5.4 End of Treatment Study Procedures

#### Final Study Visit (Day 90)

- Record results of physical examination, vital signs
- Assess ECOG performance status

- Record participant's compliance with wearing Fitbit Inspire HR device
- Provide final instructions to participant

#### 5.5 Withdrawal Visit/Discontinuation of Therapy

No end of study procedures will be required if a patient withdraws or participation is terminated early.

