# Study Summary

Title: Measuring Physical Activity in Transfusion Dependent Patients

with Myelodysplastic Syndrome (MDS)

**Précis:** This will be a single-arm, prospective, observational study that

will collect data on daily step count, heart rate, and anemiarelated symptoms in patients with red blood cell transfusion
dependent MDS. Patients will be provided with a wearable
activity monitor, which will be used to monitor daily step
count and heart rate. Devices will be paired with a centralized
data aggregation platform which will automatically collect and
store data. Anemia-related symptom and quality of life data will
be assessed using the FACT-An questionnaire at baseline
and then twice a week during the study period. Feasibility will
be measured by accrual rate, Fitbit compliance rate and study
completion rate. Acceptability will be measured by a
satisfaction survey and a brief interview at the end of 3-month

study.

**Objectives:** Primary:

• To assess the feasibility and patient acceptability of using a Fitbit to monitor daily step count and heart rate.

Secondary:

• To graph changes in daily step count, average daily resting heart rate, Fact-An score (assessed before and one day after each transfusion), and hemoglobin level.

Patients will be given an activity tracker to wear continuously

**Population:** Red blood cell transfusion dependent patients with MDS

Phase: Pilot Study

Number of Sites: 1 site (TJUH)

,

**Intervention:** for 90 days

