# 1.5 **Endpoints/Outcome Measures**

#### 1.5.1 **Primary**

 Feasibility will be measured by accrual rate, compliance with the device (80% of the 90-day intervention time), and retention rate.  Acceptability will be measured by a short survey and interview addressing participant satisfaction.

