# 3.3 Participant Withdrawal

#### 3.3.1 Reasons for Withdrawal

Participants are free to withdraw from participation in the study at any time upon request or dropped from the trial at the discretion of the investigator.

An investigator may terminate a study participant's participation in the study if:

- The subject withdraws consent.
- Investigator's decision to withdraw the subject.
- Noncompliance with trial procedure requirements.
- Administrative reasons
- Any clinical adverse event (AE), laboratory abnormality, or other medical condition or situation occurs such that continued participation in the study would not be in the best interest of the participant.
- The participant meets an exclusion criterion (either newly developed or not previously recognized) that precludes further study participation.

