#### 9 Statistical Considerations

#### 9.1 **Analysis Plans**

**Primary Analysis:** The first aim of this study is to assess the feasibility of activity monitoring. This will be defined as usage of the Fitbit device for at least 80% of the 90 days under observation. The overall study period compliance rate along with a one-sided exact 95% confidence interval will be estimated. The device will be considered to have acceptable feasibility if the lower bound of the CI is above 0.6 or, equivalently, if at least 17/21 (81%) of participants are compliant for at least 70% of the days under observation.

Accrual rate and retention rate for the study will also be calculated.

Quantitatively, participants will complete the Client Satisfaction Quesionnaire-8 item version (CSQ-8), a validated measure that elicits the client's perspective on the value of services received. Qualitatively, we will interview each participant at the end of their 90-day participation to understand their perceived barriers and facilitators of using Fitbit in their daily activities and elicit their feedback to refine future study design. Interviews will be digitally audio-recorded and transcribed verbatim. Transcripts will be analyzed with a pre-defined code book to summarize participant's experience and comments.

**Exploratory Analyses:** Descriptive statistics will be used to outline patient characteristics and report Fact-An results. We will plot daily step count, average daily resting heart rate, hemoglobin levels, and Fact-An scores. We will use multivariate analyses to identify relationships between these variables and to determine if pretransfusion step count and/or heart rate predict post-transfusion FACT-An results.

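### Acceptability, half of the primary objective, is timed for the end of 90 days, and nothing provides for collecting it from participants who leave early

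*Combined protocol and SAP*

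**What the plan says.** Sections 1.4.1 and 1.5.1 make acceptability part of the primary objective and a primary endpoint: "Acceptability will be measured by a short survey and interview addressing participant satisfaction".

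Two places give timing. The Study Summary describes a "satisfaction survey and a brief interview at the end of 3-month" study. Section 9.1 names the CSQ-8 as the survey without a separate time for it, and says of the interview: "we will interview each participant at the end of their 90-day participation to understand their perceived barriers and facilitators of using Fitbit".

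For those who do not reach Day 90, section 5.5 states: "No end of study procedures will be required if a patient withdraws or participation is terminated early". Section 3.3.2 adds: "Replacement of participants who withdraw or discontinue early in the study will be allowed". The grounds for ending participation in section 3.3.1 include "Noncompliance with trial procedure requirements", alongside withdrawal of consent, investigator decision, and medical and administrative grounds.

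The CSQ-8 and the interview are not listed among the Day 90 procedures in section 5.4, which end with "Provide final instructions to participant", or in the schedule of events in Appendix A.

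**The concern.** The interview exists to learn what hinders and helps use of the device and to improve a later study. Participants who stopped because of the device know the hindrances best, yet the plan does not provide for asking them. Failure to follow trial procedures is a listed ground for ending participation and can include not wearing the device, so the route out of the study may be linked to the outcome being measured. Replacing a leaver with someone who completes makes the gap less visible in the reported sample.

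At stake is whether a favourable acceptability result describes everyone who was given the device or only those who kept it for 90 days. The gap cannot be repaired once participants have gone.

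**Working it through.** **1. Is there any provision for leavers?** Set side by side:

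| Section | Content | Reaches early leavers? |
|---|---|---|
| Study Summary | Survey and interview at the end of three months | No |
| 9.1, CSQ-8 | Participants complete it; no time given | Not stated |
| 9.1, interview | Every participant, at the end of 90-day participation | Wording is universal, timing is not |
| 5.4 and Appendix A | Neither instrument listed | No |
| 5.5 | End-of-study procedures not required | Waived |
| 3.3.2 | Replacement allowed; nothing on the leaver's data | No |
| 13.3 | List of data types names neither the reason for leaving nor the acceptability measures | No |

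Section 5.5 does not forbid asking leavers. Nothing arranges for it, and the waiver sits uneasily with the universal wording in 9.1.

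**2. The plan's own figures.** Inputs from sections 9.1 and 9.2: 21 participants, null compliance rate 0.60, alternative 0.85, one-sided exact test at 0.05, and feasibility met "if at least 17/21 (81%) of participants are compliant".

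- At a cut-off of 17/21, exact binomial power is 0.8025 (stated: 80%) and type I error is 0.0370.
- The one-sided 95% exact lower bound is 0.616 for 17/21 (above 0.6) and 0.563 for 16/21 (below 0.6). The cut-off is right.
- Tolerance of the rule: 21 − 17 = 4, and 4/21 = 19.0%. If leavers are counted as non-compliant within the 21, four can leave with no acceptability data and feasibility is still declared.

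**3. Effect on an acceptability mean.** Let *w* be the fraction of enrolled participants who leave unasked, *m_c* and *m_l* the completer and leaver means, and *d* = *m_c* − *m_l*. Then

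completer mean − all-enrolled mean = *m_c* − [(1 − *w*)*m_c* + *w m_l*] = *w* × *d*.

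The documents give no dropout rate, so the leaver counts are assumptions; 4 matches the tolerance above.

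| Leavers (assumed) | *w*, no replacement | *w*, each replaced by a completer |
|---|---|---|
| 2 | 2/21 = 9.5% | 2/23 = 8.7% |
| 4 | 4/21 = 19.0% | 4/25 = 16.0% |
| 5 | 5/21 = 23.8% | 5/26 = 19.2% |

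**4. One illustration, with assumed satisfaction rates.** Suppose 4 of 21 leave without replacement, 90% of the 17 completers are satisfied, and 30% of leavers would have been. The survey reports 90%. The share among all 21 is (17 × 0.9 + 4 × 0.3)/21 = 16.5/21 = 79%. With leavers' views wholly unknown, it could lie anywhere from 15.3/21 = 73% to 19.3/21 = 92%.

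**The case against.** **Section 5.5 may waive less than it seems to.** Section 5.4 does not list the CSQ-8 or the interview, so 5.5 can be read as waiving only the Day 90 clinic visit, leaving the universal wording of 9.1 in force. This reading is possible. But the same sentence in 9.1 fixes the interview at the end of 90 days, and the Study Summary times both instruments there. On either reading no contact with leavers is arranged.

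**Other data will show what happened.** Retention is reported, wear before exit is on the data platform, and section 13.5 requires deviations, including participant noncompliance, to be addressed in source documents. Some device-related exits should therefore leave a record. That narrows the point. It does not cover someone who withdraws voluntarily because they dislike the device, and none of it says what leavers thought.

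**The magnitude is an identity applied to assumed counts.** This stands: *d* is unknown and may be zero. The 4/21 anchor also assumes that leavers stay in the denominator as non-compliant. Section 9.1 does not say whether replaced participants count, so the rule need not cap the number of leavers.

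**No decision turns on it.** Acceptability has no threshold or test in this small pilot. Participants who stay but wear the device little are still interviewed, so barriers are not heard only from satisfied users. Sparing ill patients exit duties is also a defensible choice. These points limit the severity, but a voluntary offer imposes no duty, and acceptability remains part of the primary objective.

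**Conclusion.** The concern holds. Followed as written, the plan would draw satisfaction and perceived barriers essentially from completers and would not systematically record why others left. Any overstatement of mean satisfaction equals the fraction leaving times the completer-minus-leaver difference: about 9% to 24% of that difference for an assumed 2 to 5 leavers. It is plausibly upward if some exits are due to the device, and small or nil if exits are medical or administrative. Without exit data or recorded reasons, a reader could not reliably tell which case applies. The formal compliance rule and its power are not touched. The change should be made, because it is cheap and the missing information cannot be recovered later.

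**What to change.** - **Section 5.5:** state that a participant who stops early will be asked, if willing, to complete the CSQ-8 and the brief interview by telephone at the time of stopping, and that the reason for stopping is recorded. Reconcile this with the universal wording and the 90-day timing in 9.1.
- **Section 9.1:** report CSQ-8 and interview results for all enrolled participants, including any later replaced. Show completers and early leavers separately, with the number not assessed and their reasons for leaving.
- **Section 5.4 and Appendix A:** list the CSQ-8 and the interview at study completion. This is a consistency correction that also protects collection from completers.

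**Cost:** an amendment, with the IRB approval that section 12.2 requires, and one short voluntary call per leaver, plus the recording and transcription that 9.1 already prescribes for interviews. The instruments are already chosen. Section 13.2 and Appendix A already have the FACT-An taken by telephone, although sections 2 and 6.1 describe it as paper or electronic, which needs reconciling separately. Some leavers will decline, so the gap is reduced, not closed.

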# 6 Study Procedures and Evaluations

#### 6.1 Study Procedures/Evaluations

The patient's medical history will be obtained from the patient and his/her medical records. A complete list of current prescription medications will be obtained. A complete physical examination including vital signs (blood pressure, heart rate, respiratory rate, pulse oximetry, temperature) will be assessed. A CBC to assess hemoglobin will be collected twice per week during the enrollment period. The CBC can be collected at TJUH or any other laboratory (Quest, LabCorp, or others). If the CBC is collected outside of TJUH, results will be obtained from the outside lab. Office visits will be scheduled per standard of care practices at the treating physician's discretion. The decision to transfuse blood will be made by the treating physician per standard of care practice. A FACT-An questionnaire will be used to assess anemia related symptoms and quality of life twice a week. The Fact-An will be completed either on paper or electronically (based on participant preference). The Fitbit device will capture daily step count and heart rate and the information will be stored in a centralized data aggregation platform.

# 6.2 Laboratory Procedures/Evaluations

#### 6.2.1 Clinical Laboratory Evaluations

A CBC to assess hemoglobin will be collected twice per week during the enrollment period. The CBC can be collected at TJUH or any other laboratory (Quest, LabCorp, or others). If the CBC is collected outside of TJUH, results will be obtained from the outside lab either electronically or on paper.

# 7 Evaluation of Safety

# 7.1 Specification of Safety Parameters

# 7.1.1 Unanticipated Problems

Unanticipated problems (UAPs) include, in general, any incident, experience, or outcome that meets the following criteria:

unexpected in terms of nature, severity, or frequency given (a) the research
procedures that are described in the protocol-related documents, such as the
IRB-approved research protocol and informed consent document; and (b) the
characteristics of the participant population being studied;

UAPs are considered to pose risk to participants or others when they suggest that the research places participants or others at a greater risk of harm (including physical, psychological, economic, or social harm) than was previously known or recognized.

# 7.2 Safety Reporting

#### 7.2.1 Reporting to IRB

### 7.2.1.1 Unanticipated Problems

All incidents or events that meet criteria for unanticipated problems (UAPs) as defined in Section 7.1.1 Unanticipated Problems require the creation and completion of an unanticipated problem report form (OHR-20).

UAPs that pose risk to participants or others, and that are not AEs, will be submitted to the IRB on an OHR-20 form via the eazUP system within 10 working days of the investigator becoming aware of the event.

UAPs that do not pose risk to participants or others will be submitted to the IRB at the next continuing review.

# 8 Study Oversight

The study PI is responsible for the study oversight. The PI will ensure that the rights of human participants are protected, that the study is implemented in accordance with the protocol and/or other operating procedures, and that the quality and integrity of study data and data collection methods are maintained.

#### 9 Statistical Considerations

#### 9.1 **Analysis Plans**

**Primary Analysis:** The first aim of this study is to assess the feasibility of activity monitoring. This will be defined as usage of the Fitbit device for at least 80% of the 90 days under observation. The overall study period compliance rate along with a one-sided exact 95% confidence interval will be estimated. The device will be considered to have acceptable feasibility if the lower bound of the CI is above 0.6 or, equivalently, if at least 17/21 (81%) of participants are compliant for at least 70% of the days under observation.

Accrual rate and retention rate for the study will also be calculated.

Quantitatively, participants will complete the Client Satisfaction Quesionnaire-8 item version (CSQ-8), a validated measure that elicits the client's perspective on the value of services received. Qualitatively, we will interview each participant at the end of their 90-day participation to understand their perceived barriers and facilitators of using Fitbit in their daily activities and elicit their feedback to refine future study design. Interviews will be digitally audio-recorded and transcribed verbatim. Transcripts will be analyzed with a pre-defined code book to summarize participant's experience and comments.

**Exploratory Analyses:** Descriptive statistics will be used to outline patient characteristics and report Fact-An results. We will plot daily step count, average daily resting heart rate, hemoglobin levels, and Fact-An scores. We will use multivariate analyses to identify relationships between these variables and to determine if pretransfusion step count and/or heart rate predict post-transfusion FACT-An results.

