# 9.2 Sample Size Considerations

A sample size of 21 patients provides 80% power to reject the null hypotheses that the true compliance rate is less than or equal to 60% using a one-sided exact binomial tests of size 0.05 assuming the true rate is 85% or greater.

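### The feasibility rule counts participants at 70% of days although the endpoint is defined at 80%, so the same data can pass or fail

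*Combined protocol and SAP*

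**What the plan says.** Three statements set how much wear makes a participant compliant.

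- Section 1.5.1, primary endpoints: "compliance with the device (80% of the 90-day intervention time), and retention rate".
- Section 9.1, primary analysis, definition of feasibility: "This will be defined as usage of the Fitbit device for at least 80% of the 90 days under observation".
- Section 9.1, same paragraph, decision rule. Its count form reads "if at least 17/21 (81%) of participants are compliant for at least 70% of the days under observation". The plan offers this as the equivalent of an interval form, in which the lower confidence bound must exceed 0.6.

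Between the last two, 9.1 says which estimate is to be judged: "The overall study period compliance rate along with a one-sided exact 95% confidence interval will be estimated".

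Section 9.2 plans 21 participants for 80% power against a null compliance rate of at most 60%. The test and the alternative are described there in these terms: "using a one-sided exact binomial tests of size 0.05 assuming the true rate is 85% or greater". Section 9.2 does not say what share of days makes a participant compliant. Nothing elsewhere in the document explains the 70% figure.

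**The concern.** The compliance rate behind the confidence interval takes its meaning from the 80% definition just before it and from 1.5.1. The 17/21 count explicitly uses 70%. These are two different endpoints, and the second is easier to meet. A participant with 63 to 71 worn days is compliant under one sentence and non-compliant under the other.

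This is the only pass/fail rule in the study. Accrual and retention are only to be calculated, and acceptability has no stated threshold. If the rule stays ambiguous, the threshold could be settled after the data are known. That risk is real here, because section 11 has the study team reviewing activity logs weekly.

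The denominator wording also varies. Section 1.5.1 and the definition in 9.1 name 90 days, while the decision rule refers to observed days without a number. For someone who leaves early, it is unclear whether the base is still 90 days.

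**Working it through.** **Inputs.** n = 21, null rate 0.60, alternative 0.85, one-sided exact test of size 0.05 (section 9.2). Cut-off 17/21, lower bound above 0.6, one-sided exact 95% interval, thresholds of 80% and 70% (section 9.1). Observation period of 90 days (sections 1.5.1 and 9.1).

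**1. Reproduce the plan's figures, with one definition of compliant.** The chance of passing is

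P(X ≥ 17 | p) = Σ (k = 17 to 21) C(21, k) p^k (1 − p)^(21 − k).

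- At p = 0.60: 0.0370, below the stated size of 0.05.
- At p = 0.85: 0.8025, matching the stated 80% power.

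**2. Check the equivalence claimed in 9.1.** The one-sided 95% exact (Clopper-Pearson) lower bound for r successes is the 5th percentile of a Beta(r, 21 − r + 1) distribution.

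- r = 17, Beta(17, 5): 0.6156, above 0.6.
- r = 16, Beta(16, 6): 0.5630, below 0.6.

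So 17 is the smallest passing count. The interval rule and the count rule agree, provided both count the same participants.

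**3. Convert the thresholds to days.** 0.80 × 90 = 72 days and 0.70 × 90 = 63 days. The disputed band is 63 to 71 days.

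**4. One data set, two verdicts.** Take 14 participants with 72 or more days, 3 with 63 to 71, and 4 with fewer than 63 (14 + 3 + 4 = 21).

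- 80% definition: 14/21. The lower bound from Beta(14, 8) is 0.464, so the study fails.
- 70% definition: 14 + 3 = 17/21. The lower bound is 0.616, so the study passes.

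**5. Effect on the error rate if the null concerns the 80% endpoint but success is counted at 70%.** Let 0.60 be the true share reaching 80% of days and q the share between 70% and 80%. The document gives no wear-time distribution, so q is assumed. The share counted as compliant is 0.60 + q.

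| q (assumed) | Share counted | P(17 or more of 21) |
|---|---|---|
| 0 | 0.60 | 0.037 |
| 0.05 | 0.65 | 0.092 |
| 0.10 | 0.70 | 0.198 |
| 0.15 | 0.75 | 0.367 |
| 0.20 | 0.80 | 0.586 |

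**6. The opposite mix.** Suppose the 85% planning rate was meant for the 70% threshold but the verdict uses 80%. With q = 0.05 the share counted is 0.85 − 0.05 = 0.80, and with q = 0.10 it is 0.75. From the same tail probabilities, power falls from 0.8025 to 0.586 or 0.367.

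**The case against.** The strongest reply is that the word of equivalence joins the lower-bound rule to the 17/21 count, and that this equivalence is correct for n = 21. The plan never says outright that 70% and 80% are the same. Used consistently, either threshold gives a valid test with size 3.7% and power 80.25%. The inflated error rates arise only when the two are mixed, and they depend on assumed shares; the 59% figure needs one participant in five to fall inside a nine-day window. Two of the three statements say 80%, so a drafting slip is plausible. The study is a small observational pilot whose result drives no treatment decision.

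Much of this is fair. The cut-off and sample size are sound, and the figures in step 5 show sensitivity rather than estimate the plan's actual error. Verdicts differ only when the disputed band moves the count from 16 or fewer to 17 or more. The denominator wording may be shorthand for the same 90 days; it is an ambiguity, and the main point does not rest on it.

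The contradiction remains. The mixed case is what the text literally sets out: an interval on an 80% endpoint, matched to a count at 70%. Nothing in the document says which figure governs, and a formal test with stated size and power needs one definition of success.

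**Conclusion.** The concern holds. The primary decision rule carries two per-participant thresholds, 72 and 63 of 90 days, and either can be claimed as the plan. Opposite verdicts on the same data are possible, as the 14/3/4 example shows without any distributional assumption. If the 70% count is applied to the 80% endpoint at its null boundary, the chance of a false pass rises from 3.7% to between 9% and 59% for assumed band shares of 5% to 20%. The error has no effect on n = 21 or on 17 as the cut-off. It should be corrected before analysis because it affects the study's only formal criterion.

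**What to change.** Use one threshold and one denominator throughout.

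- **If 80% is intended**, as 1.5.1 and the definition in 9.1 suggest: reword the decision rule in 9.1 so that feasibility requires at least 17 of 21 participants to have used the device on 72 or more of the 90 days.
- **If 70% is intended**: change 1.5.1 and the definition in 9.1 to 63 or more of the 90 days, and leave the count rule at 70%.
- **In either case**: say in 9.2 that the 60% null and 85% alternative refer to that definition, and confirm that the base is 90 days for participants who stop early.

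Make the change before compliance is tabulated at either threshold. Because activity logs are reviewed weekly, record how much follow-up had accrued when the choice was made. Reporting the other threshold as a sensitivity analysis is useful but is not needed to remove the contradiction.

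The cost is a short wording amendment with the IRB review that section 12.2 requires. Sample size, cut-off and data collection do not change. If 80% is kept, passing is somewhat harder than under the 70% sentence. If 70% is chosen, the primary endpoint becomes easier than the one now given in 1.5.1.
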